7.6 Methods for Clinical Procedures

Not applicable.

8. CRITERIA FOR EVALUATION AND ENDPOINT DEFINITION

8.1 Primary Endpoint

- 8.1.1 To determine the effect of PROSTVAC® on the change (pre to post-intervention) in CD8⁺ positive cells in the stroma adjacent to tumor and within the malignant portion of the prostate biopsies. The change will be compared between participants treated with PROSTVAC® and those treated with placebo. A subgroup analysis will be performed to compare the change in CD8⁺ positive cells between study groups in specimens collected by targeted biopsy.
- 8.1.2 To determine the effect of PROSTVAC® on the change in CD4⁺ positive cells in the stroma adjacent to tumor and within the malignant portion of the prostate biopsies. The change will be compared between participants treated with PROSTVAC® and those treated with placebo. A subgroup analysis will be performed to compare the change in CD4⁺ positive cells between study groups in specimens collected by targeted biopsy.

8.2 Secondary Endpoints

- 8.2.1 To assess the effect of PROSTVAC® on the change in PD-L1 positive cells in the stroma adjacent to tumor and within the malignant portion of the prostate biopsies. The change will be compared between participants treated with PROSTVAC® and those treated with placebo. A subgroup analysis will be performed to compare the change in PD-L1 positive cells between study groups in specimens collected by targeted biopsy.
- 8.2.2 To assess the correlation between the change in CD8⁺ and the change in PSA. The correlation between the change in CD8⁺ in the stroma adjacent to tumor and within the malignant portion of the prostate biopsies and the change in PSA (from baseline to 6 months (5-7 months) post-intervention) in participants treated with PROSTVAC® will be examined.
- 8.2.3 To assess the effect of PROSTVAC® on the change in CD8⁺, CD4⁺, and PD-L1 positive cells in the benign portion of the prostate biopsies. The change will be compared between participants treated with PROSTVAC® and those treated with placebo.
- 8.2.4 To assess the effect of PROSTVAC® on the change in PSA. The change in PSA from baseline to 6 months (5-7 months) post-intervention will be compared between participants treated with PROSTVAC® and those treated with placebo.
- 8.2.5 To assess the effect of PROSTVAC® on tumor grade progression, defined as a post-intervention

- Gleason score of $\geq 4+3$ using all biopsy data, i.e., from random and target biopsy cores. Proportion of men with post-intervention Gleason score of $\geq 4+3$ will be compared between the treatment groups. In addition, this endpoint will be evaluated in the subgroup of patients in whom MRI-targeted biopsies were obtained pre- and post-intervention.
- 8.2.6 To assess the effect of PROSTVAC on tumor extent based on the percent of positive random biopsy cores. The change in tumor extent will be compared between the treatment groups.
 - 8.2.7 To assess the proportion of men with no cancer in the post-intervention biopsy between participants treated with PROSTVAC® and those treated with placebo. This analysis will utilize all biopsy data, i.e., from random and target biopsy cores.
 - 8.2.8 To assess the effect of PROSTVAC on the size of the dominant lesion on MRI (largest histopathologically confirmed lesion) in the subgroup of patients with MRIs pre and post-intervention.
 - 8.2.9 To determine the safety and feasibility of PROSTVAC® in patients with clinically localized prostate cancer undergoing active surveillance.
 - 8.2.10 To assess the change in circulating 15-Mer PSA-specific T cells.
 - 8.2.11 To assess the change in soluble antibodies to tumor-associated antigens.
 - 8.2.12 To assess the immunologic effects of PROSTVAC® on the target organ using multiplex immunofluorescence.
 - 8.2.13 To assess the effects of PROSTVAC on LUTS by evaluating changes in International Prostate Symptom Score from baseline to 6 months (5-7 months) post-intervention.

If feasible, change in tumor grade and extent will be assessed by central pathology review.

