On 14, 28, 56, 84, 112, 140 days following the Baseline Visit, participants will return for interim study visits. Participants will receive booster vaccinations with subcutaneous injection of PROSTVAC-F or placebo, injected into the upper outer thigh or upper arm. It is recommended to alternate the injection sites. Prior to the first booster injection, participants will be evaluated for evidence of bacterial infection, blisters, vesicles or evidence of persistent infection. Weight, vital signs, AEs and conmed information will be collected at each interim visit. At the Day 84 visit, International Prostate Symptom Score will be obtained and blood will be drawn for PSA, CBC-diff, and CMP prior to administration of the vaccine injection. CBC-diff and CMP will need to be evaluated to determine whether the injection on that day may be given or omitted and whether there is the need to repeat safety labs before the next scheduled injection. If needed, the labs can be done on a different day prior to the day for the vaccine injection, but the labs and the vaccine injection should fall within the window specified on the schedule of events. The Day 14 visit can be scheduled +/- 5 days. The Day 28, 56, 84, 112, 140 interim visits can be scheduled +/- 7 days. The vaccine injection may be omitted due to adverse events (as described in section 5.6).

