7.4 Evaluation at Completion of Study Intervention

Seven to fourteen days after the last scheduled vaccine dose, participants will return for the post-intervention visit. Blood will be collected for CBC-diff, CMP, PSA, PBMCs, and serum prior to the digital rectal exam and collection of the post-intervention biopsy. Participants will be evaluated for weight, vital signs, AEs and concomitant medications. International Prostate Symptom Score will be obtained. DRE will be performed at the discretion of the individual urologist. TRUS-guided prostate biopsy or targeted prostate biopsy using MR-US fusion will be performed as part of the routine care of patients on active surveillance.

Pre- and post-intervention biopsy pathology reports will be collected, de-identified, labeled with study ID and participant ID and submitted to the University of Arizona Early Phase Chemoprevention Consortium Office.

Report Submission Information:
University of Arizona Early Phase Chemoprevention Consortium Office
Attn: [name]
[name]
[name]
[contact]
[contact]
Email: [contact]

Unstained tissue slides from the pre- and post-intervention prostate biopsies will be requested from the institutional pathology lab for analysis of the immunologic response in the target tissue.

If available, reports from the prostate MRI scans (and companion pathology reports) performed from 3 years prior to and 6 months after the study intervention will be collected. Reports will be de-identified, labeled with study ID and participant ID and submitted to the University of Arizona Early Phase Chemoprevention Consortium Office to capture the lesion size information.

The results of all PSA tests performed throughout the intervention as part of the routine care of patients on active surveillance will be collected.

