7.5 Post-intervention Follow-up Period

Study subjects will be followed for 30 days after the last study dose is given. Participants will continue to record adverse events during the 30-day follow-up period. The diary will be mailed back to the study staff in a pre-addressed, stamped envelope. Study staff will contact the subject by phone to clarify any of the diary entries, if necessary.

Participants will return for a follow-up visit 6 months (5-7 months) after the post-intervention biopsy or 6 (5-7 months) months after the last study dose is given, if no post-intervention biopsy was performed, as part of the standard-of-care. Blood will be collected for PSA. Participants will be interviewed for interval medical history including autoimmune disease. International Prostate Symptom Score will be assessed and active surveillance status will be documented. DRE will be performed at the discretion of the individual urologist. Patients who have undergone prostatectomy, radiation therapy or focal prostate cancer therapy are exempt from the six-month follow-up visit requirement.

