10.2 Collection and Handling Procedures

Blood Samples

Clinical labs

Approximately 10 ml of blood will be drawn to one 3 ml EDTA and one 7 ml SST or tiger top Vacutainer tubes at screening, Day 84, and at the post intervention for CBC with differentials and CMP. The EDTA tube will be gently inverted to mix for anticoagulation. The SST tube will be held at room temperature for 30 min and then centrifuged. Blood tubes will be prepped, labeled, and packaged according to the recommendations from the diagnostic laboratory.

PSA

Approximately 4 ml of blood will be drawn into one SST or tiger top Vacutainer tube at screening, baseline, Day 84, and at the end of intervention. The SST tube will be held at room temperature for 30 min and then centrifuged. Blood tubes will be prepped, labeled, and packaged according to the recommendations from the diagnostic laboratory.

PBMC

Approximately 60 ml of blood will be drawn into multiple Heparin Vacutainer tubes at baseline and at the end of intervention. The tubes will be labeled with study ID, subject ID, and visit date. The tubes will be gently inverted to mix for anticoagulation and shipped overnight at ambient temperature to a central laboratory for PBMC isolation.

Serum

Approximately 5 ml of blood will be drawn into a SST or tiger top Vacutainer tube at baseline and at the end of intervention. The SST tube will be held at room temperature for 30 min and then centrifuged. Serum will be aliquoted evenly into ten cryovials (~200 µl each) and stored at -80°C. The cryovials will be labeled with study ID, subject ID, and visit date.

Tissue Sections

Unstained tissue slides from pre and post intervention prostate biopsies will be requested from each institution's pathology department for measurement of tissue biomarkers. One to two tissue blocks with tumor from pre-intervention biopsy and same number of tissue blocks with tumor from post-intervention biopsy will be selected to cut the tissue slides. If no tumor was present in the post-intervention biopsy, block(s) from the same tissue region as the pre-intervention block(s) with tumor will be selected. Five to 10 unstained slides will be requested from each block.

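### The PSA and IPSS comparisons rest on a 6-month visit from which men given definitive therapy are exempt, and the plan does not say how these men are handled or use their scheduled earlier values

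*Combined protocol and SAP*

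**What the plan says.** All references are to the combined protocol and SAP.

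- **Endpoints.** 8.2.4 reads "The change in PSA from baseline to 6 months (5-7 months) post-intervention will be compared between participants treated with" PROSTVAC and those given placebo. 8.2.13 assesses urinary symptoms through "changes in International Prostate Symptom Score from baseline to 6 months (5-7 months) post-intervention". 8.2.2 correlates the CD8 change with the same 6-month PSA change in the vaccine arm. Section 13.5 lists PSA and IPSS change without a time point and adds no other.
- **Exemption.** Section 7.5: "Patients who have undergone prostatectomy, radiation therapy or focal prostate cancer therapy are exempt from the six-month follow-up visit requirement". Section 3 and a footnote to the schedule in 7.1 repeat it. The visit falls 6 months after the post-intervention biopsy, or after the last dose if there was no biopsy.
- **Earlier PSA values.** Section 10.2 has PSA drawn into one "SST or tiger top Vacutainer tube at screening, baseline, Day 84, and at the end of intervention".
- **Earlier IPSS values.** IPSS is taken at screening, at Day 84 and at the post-intervention visit (7.1). Section 7.3: "At the Day 84 visit, International Prostate Symptom Score will be obtained and blood will be drawn for PSA".
- **Order at the post-intervention visit.** Section 7.4: "Blood will be collected for CBC-diff, CMP, PSA, PBMCs, and serum prior to the digital rectal exam" and the biopsy. No order relative to the biopsy is stated for IPSS.
- **Analysis.** Section 13.5 plans a two-sided two-sample t test at 5% for each secondary endpoint, labelled exploratory. Section 13.1 puts all analyses on the intent-to-treat principle, with multiple imputation where judged necessary, and 13.5 repeats this for the secondary endpoints. Section 13.5 also expects at least 25% missing, will compare missing rates by arm, and will model predictors of missingness.

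**The concern.** The post-intervention biopsy and PSA are results that can lead to surgery, radiation or focal therapy in the following months. A man treated on that basis is not due at the only visit that supplies his PSA and IPSS endpoints. His value is therefore missing for a reason connected with the outcome. If the vaccine affects progression, the proportion missing may differ by arm. Leaving out placebo men with unfavourable PSA courses would make the placebo mean look better and hide a benefit.

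Exemption from a requirement does not bar attendance. If a treated man does have a 6-month PSA, it reflects the therapy. The plan has no rule for such a value, and a literal intent-to-treat comparison would admit it. Nor does the plan say whether the target is PSA in the absence of definitive therapy or PSA regardless of it.

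Useful data are already scheduled. These men should have PSA at Day 84 and at the post-intervention visit, the latter drawn before the biopsy. The t test on 6-month change uses neither. PSA change is one of the trial's clinical indicators of progression, and the correlation in 8.2.2 inherits the problem.

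**Working it through.** **1. The plan's own figure.** None is stated for PSA or IPSS. The only sample-size calculation (13.4) concerns the tissue endpoints. Its numbers reproduce (100 × 0.9 × 0.7 = 63; 50 × 0.9 × 0.7 = 31.5, taken as 31), but this point does not depend on them.

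**2. What an exempt man contributes.**

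| Visit | PSA | IPSS | Used in the planned t test? |
|---|---|---|---|
| Screening / baseline | both | screening only | yes, as the starting value |
| Day 84 | yes | yes | no |
| Post-intervention | yes, before biopsy | yes | no |
| 6 months | not required | not required | yes, the only follow-up value |

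He enters the comparison only if imputation is carried out. The interim values help only if the analyst chooses to include them.

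**3. How many men.** The documents give no 6-month treatment rate. Section 2.1 says up to one-third are treated within 2 to 5 years of starting surveillance, which does not convert to a 6-month rate in this trial. The range of 5–20% of placebo men exempt is therefore an assumption.

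**4. Illustrative bias of an observed-case comparison.** From the documents: 150 men randomized 2:1 and 10% attrition, giving 90 and 45. Assumed, not in the documents:
- the vaccine lowers the post-intervention PSA change by 0.3 SD;
- that change correlates 0.8 with the 6-month change;
- men above a common cut-off *c* of post-intervention change are treated and have no 6-month value.

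Full-data 6-month difference: 0.8 × (−0.3) = −0.24 SD.

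Observed-case difference: 0.8 × [−0.3 − λ(c + 0.3) + λ(c)], where λ(u) = φ(u)/Φ(u).

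| Placebo exempt | Vaccine exempt, 1 − Φ(c + 0.3) | c | λ(c) | λ(c + 0.3) | Observed-case difference | Shrinkage |
|---|---|---|---|---|---|---|
| 5% | 2.6% | 1.645 | 0.109 | 0.062 | −0.20 | 16% |
| 10% | 5.7% | 1.282 | 0.195 | 0.121 | −0.18 | 25% |
| 20% | 12.7% | 0.842 | 0.350 | 0.238 | −0.15 | 37% |

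A simulation of 4,000 trials per row gave −0.200, −0.178 and −0.145 against simulated full-data differences of −0.239, −0.240 and −0.235. That is shrinkage of 16%, 26% and 38%, which agrees within simulation error.

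**5. Effect of using the interim value.** Filling in the missing 6-month values by regression on the post-intervention value and arm gave −0.24 SD in all three cases. This is expected, because missingness here depends only on that value.

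**6. Precision.** The difference detectable with 80% power at two-sided 5% is (1.960 + 0.842) × √(1/n₁ + 1/n₀):
- no one exempt, 90 and 45: 0.51 SD;
- 5% exempt in both arms, 85.5 and 42.75: 0.52 SD;
- 10%, 81 and 40.5: 0.54 SD;
- 20%, 72 and 36: 0.57 SD.

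Loss of precision is small. Selection is the main issue.

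**The case against.** The strongest reply is that the plan already provides for missing data. A reader might infer from the exemption that men who progress simply drop out of both comparisons. The documents do not support that. Sections 13.1 and 13.5 keep every randomized man in the analysis in principle, allow imputation for secondary endpoints, compare missing rates by arm and look for predictors of missingness. Section 13.4 puts such predictors into the imputation model; it is written for the primary endpoints, and 13.5 refers back to it. An imputation using post-intervention PSA would remove the bias in step 4. The exemption also follows therapy, not progression: an untreated man who has progressed is still due at 6 months, and a man may choose treatment without progressing.

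This narrows the point but does not close it. Imputation is optional with no stated trigger, no PSA or IPSS visit is named as an input, and imputation does nothing about an observed value already altered by therapy.

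A second tempting reading is that a post-therapy PSA will be counted as a vaccine effect. The plan does not say so. It is silent, and the silence is the gap.

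It is also fair to say that a repeated-measures model is not automatically better than imputation. A model using only the PSA series omits the biopsy result, a likely trigger for therapy, whereas imputation can include it. Finally, no bias has been shown for IPSS: nothing in the documents links an oncologic decision to treat with the urinary-symptom course beforehand.

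**Conclusion.** The point holds for PSA, in 8.2.4 and 8.2.2, as a gap in definition and a weak choice of analysis. Men given definitive therapy have no planned 6-month value, remain in the analysis only through an unspecified and optional imputation, and have no rule for values obtained after therapy. For IPSS the same gap in wording exists, but the case for material bias is weaker.

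The size cannot be derived from the documents. The 16–38% shrinkage rests on the assumed exempt rates, 0.3 SD effect, 0.8 correlation and cut-off rule, and on an observed-case analysis that the plan does not commit to. It shows direction and plausible order, not an expected bias. No PSA standard deviation is given, so a size in ng/mL would also be conjecture.

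The primary tissue endpoints are unaffected, and 13.5 labels the secondary analyses exploratory. The impact is limited: a cheap improvement.

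**What to change.** Change the wording of 8.2.4, 8.2.13 and 13.5, and add a line to 8.2.2:

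- **(a) Post-intervention comparison.** Add a between-arm comparison of PSA at the post-intervention visit, drawn before the biopsy, adjusted for the baseline value and the stratification factors. Report it beside the 6-month result.
- **(b) 6-month comparison.** State that PSA after definitive therapy is treated as missing, so the target is PSA in the absence of such therapy. Apply the same rule at any visit where therapy came first. Replace the unadjusted t test with a repeated-measures model over Day 84, post-intervention and 6 months, or with multiple imputation that includes the Day 84 and post-intervention values and the post-intervention biopsy result. Imputation has the advantage of using the biopsy result. State the handling of IPSS in the same way.
- **(c) Correlation.** Repeat 8.2.2 with the PSA change to the post-intervention visit.
- **(d) Reporting.** Give the number of exempt men by arm, and how many of them had a PSA or IPSS value after therapy.

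The cost is a little more analysis; no visit, sample or assessment is added. The 6-month result still assumes data missing at random given the earlier values. The post-intervention comparison depends much less on that assumption, which is why the two should be shown together.

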1.2 Secondary Objectives (prioritized list)

- 1.2.1 To assess the effect of PROSTVAC® on PD-L1 positive cells in the stroma adjacent to tumor and within the malignant portion of the prostate biopsies.
- 1.2.2 To assess the correlation between the change in CD8⁺ and the change in PSA.
- 1.2.3 To assess the effect of PROSTVAC® on CD8⁺, CD4⁺, and PD-L1 positive cells in the benign portion of the prostate biopsies.
- 1.2.4 To assess the effect of PROSTVAC® on the change in PSA.
- 1.2.5 To assess the effect of PROSTVAC® on tumor grade (Gleason score).
- 1.2.6 To assess the effect of PROSTVAC on tumor extent (percent of positive random biopsy cores).
- 1.2.7 To compare the proportion of men on the two study arms with no cancer on post-intervention biopsy.
- 1.2.8 To assess the effect of PROSTVAC on the size of the dominant lesion on MRI (largest histopathologically confirmed lesion) in the subgroup of patients with MRIs pre and post-intervention.
- 1.2.9 To assess the effect of PROSTVAC® on circulating 15-Mer PSA-specific, MUC-1 and Brachyury-specific T cells.
- 1.2.10 To assess the effect of PROSTVAC® on soluble antibodies to tumor-associated antigens.
- 1.2.11 To assess the immunologic effects of PROSTVAC® in prostate tissue using multiplex immunofluorescence.
- 1.2.12 To assess the safety and feasibility of PROSTVAC® in the active surveillance population.
- 1.2.13 To assess the effect of PROSTVAC® on lower urinary tract symptoms (LUTS) in the active surveillance population.

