4. PARTICIPANT SELECTION

4.1 Inclusion Criteria

- 4.1.1 Biopsy-proven (consisting of ≥ 10 tissue cores) adenocarcinoma of the prostate with cancer present in at least one biopsy core, either random or targeted, in the most recent biopsy.
- 4.1.2 All prior biopsies must meet the following: $\leq 50\%$ of the total number of random biopsy cores positive for cancer
 - Gleason score $\leq (3+4)$
- 4.1.3 Clinical stage $\leq T2a$ by DRE
- 4.1.4 Biopsies performed at outside institutions should have Gleason score confirmed at the study site by a GU pathologist to ensure eligibility.
- 4.1.5 Pre-intervention biopsy tissue (most proximal to enrollment) containing sufficient tumor tissue to cut 5-10 unstained slides confirmed to be available upon request.
- 4.1.6 Screening serum PSA < 20 ng/mL. For men treated with 5-alpha-reductase inhibitors (e.g., finasteride, dutasteride), PSA needs to be < 10 ng/mL.
- 4.1.7 Hematological eligibility parameters:
Neutrophil count $\geq 1,200/\text{mm}^3$ (≥ 1.2 k/ μL)
Stable platelet count $\geq 75,000/\text{mm}^3$ (≥ 75 k/ μL)
- 4.1.8 Hepatic and renal function eligibility parameters:
Bilirubin ≤ 1.5 mg/dL (or ≤ 3.0 mg/dL for patients with Gilbert's syndrome)
ALT and AST ≤ 2.5 x ULN
Serum creatinine ≤ 1.5 x ULN
- 4.1.9 Karnofsky $\geq 70\%$; see Appendix A.
- 4.1.10 Must agree to use medically acceptable barrier and/or chemical method of contraception while on study and for at least one month following the last vaccine injection because the effects of PROSTVAC® on the developing human fetus at the recommended therapeutic dose are unknown. Should a participant's partner become pregnant or suspect she is pregnant while the participant is participating in this study, the study physician should be informed immediately. In the event a participant's partner becomes pregnant, the study sponsor may request additional information regarding the course of the pregnancy and if the pregnancy is carried to term, the birth of the child (i.e., the outcome of the pregnancy).
- 4.1.11 Ability to understand and the willingness to sign a written informed consent document.
- 4.1.12 No planned prostate biopsies during the intervention until after the post-intervention biopsy.
- 4.1.13 Men on stable doses of 5-alpha reductase inhibitors are eligible as long as there is no planned dose change while on study.

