13.2 Randomization/Stratification

We plan to randomize 150 eligible participants to receive either PROSTVAC® or matched placebo at a 2:1 ratio (i.e. 100 receiving PROSTVAC® and 50 receiving placebo) based on a random allocation rule. Blocking technique with a size of 3 or 6 will be used to assure a 2:1 ratio between PROSTVAC® and placebo. In addition, randomization will be stratified by the study site and the number of repeat biopsy following diagnosis (≤ 2 or > 2).

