13.5 Secondary Objectives, Endpoints, Analysis Plans

The secondary objectives are to determine the effects of PROSTVAC® on the change in PD-L1 positive cells in the stroma adjacent to tumor and within the malignant portion of the prostate biopsies, the correlation between the change in CD8⁺ and the change in PSA, to determine the effect of PROSTVAC® on the change in CD8⁺, CD4⁺, and PD-L1 positive cells in the benign portion of the prostate biopsies, to determine the effect of PROSTVAC® on the change in PSA, to assess the effect of PROSTVAC® on tumor grade and tumor extent, to assess the proportion of men with no cancer on the post-intervention biopsy, to assess the safety and feasibility of PROSTVAC®, and to assess the effects of PROSTVAC® on LUTS.

The secondary endpoints include the change in PD-L1 positive cells in the stroma adjacent to tumor and within the malignant portion of the prostate biopsies, the correlation between the change in CD8⁺ and the

change in PSA, the change in CD8⁺, CD4⁺, and PD-L1 positive cells in the benign portion of the prostate biopsies, the change in PSA, the tumor grade progression, the change in tumor extent, safety and feasibility, and the change in International Prostate Symptom Score. In addition, a comparison will be made between the two study arms on the proportion of patients with no cancer on the post-intervention biopsy. Similarly, MI techniques will be performed, as necessary. A two-sided two-sample t test at a significance level of 5% will be performed to compare each of the secondary endpoints between the PROSTVAC® and placebo groups. Pearson correlation coefficient will be derived to evaluate the correlation between the change in CD8⁺ and the change in PSA for participants treated with PROSTVAC®. Fisher's exact test will be performed to compare the proportion of patients with no cancer on the post-intervention biopsy and the proportion of men with an increase in Gleason score to $\geq 4+3$ between the two groups. These secondary analyses are considered exploratory, therefore, no correction will be performed for multiple comparisons.

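### Tumor grade is tested only as Gleason ≥4+3 without using entry grade; stratify that test and add an ordered-grade analysis

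*Combined protocol and SAP*

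**What the plan says.** - **Objective (1.2.5):** "To assess the effect of PROSTVAC® on tumor grade (Gleason score"). No threshold is named.
- **Entry (4.1.2):** all prior biopsies must satisfy "Gleason score $\leq (3+4"), so men enter at 3+3 or 3+4.
- **Endpoint (8.2.5):** "Proportion of men with post-intervention Gleason score of $\geq 4+3$ will be compared between the treatment groups", using random and targeted cores together.
- **Analysis (13.5):** Fisher's exact test compares "the proportion of men with an increase in Gleason score to $\geq 4+3$ between the two groups". No covariate or stratum is named.
- **Randomization (13.2):** stratified by site and number of repeat biopsies, not by entry grade.
- **Related endpoints:** clearance to no cancer is a separate endpoint (8.2.7) with its own comparison in 13.5: "Fisher's exact test will be performed to compare the proportion of patients with no cancer on the post-intervention biopsy". Tumor extent (8.2.6) is analysed as a change. The closing line of 8.2 mentions change in grade by central review if feasible, but 13.5 gives no analysis for it.
- **Status (13.5):** "These secondary analyses are considered exploratory, therefore, no correction will be performed for multiple comparisons".

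No expected ≥4+3 rate, event count or power is given for this endpoint.

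**The concern.** The endpoint is narrower than its objective. The cut lies just above the entry ceiling, so a man entering at 3+4 is one step from an event and a man entering at 3+3 is two steps away. Movement between 3+3 and 3+4, in either direction, does not register. The two entry grades probably carry different risks of reaching ≥4+3. Entry grade is neither a randomization stratum nor a term in the test, so a chance imbalance in the 3+3/3+4 mix goes uncorrected and the precision that entry grade could bring is lost. Pre-intervention pathology reports are already collected (7.4).

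Section 2.3 hypothesizes that the vaccine prevents or delays progression, and grade is a direct pathological measure of that. A null result on this single cut could be reported as no effect on grade when only part of the grade scale was examined.

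**Working it through.** **What is counted.** Post-intervention result by entry grade:

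| Entry | No cancer | 3+3 | 3+4 | ≥4+3 |
|---|---|---|---|---|
| 3+3 | non-event (see 8.2.7) | non-event | non-event, although a rise | event |
| 3+4 | non-event (see 8.2.7) | non-event, although a fall | non-event | event |

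Because 4.1.2 caps entry at 3+4, the 8.2.5 wording (score at or above 4+3) and the 13.5 wording (an increase to that level) pick out the same men.

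**Numbers of men.** Section 13.2 plans 100 and 50. With the 10% attrition in 13.4, 100 × 0.9 = 90 and 50 × 0.9 = 45 are biopsied. Multiplying by the projected 70% with tumor gives 63 and 31.5, which matches the plan's 63 and 31. I use 90 and 45, counting men with no cancer as non-events; the documents do not state this. The only power figure in 13.4 concerns CD8 and CD4, so the plan has no figure to reproduce for grade.

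**Exact Fisher power when the vaccine halves the rate.** Method: full binomial enumeration, two-sided 5%. That level is stated for the t tests and assumed here. Expected events = 45p + 90(p/2) = 90p.

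| Assumed placebo rate p | Total events | Power |
|---|---|---|
| 5% | 4.5 | 11% |
| 10% | 9 | 17% |
| 20% | 18 | 32% |
| 30% | 27 | 48% |
| 40% | 36 | 64% |

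**Threshold test against ordered grade.** Assumed placebo distribution (none / 3+3 / 3+4 / ≥4+3): entry 3+3, 35/45/15/5%; entry 3+4, 20/25/40/15%; 30% of men enter at 3+4. The placebo ≥4+3 rate is 0.7 × 5% + 0.3 × 15% = 8%, or 45 × 0.08 = 3.6 events. Under an odds ratio of 2 toward lower grade, the vaccine rates are 0.0526/2 = 0.0263 in odds, or 2.6%, for entry 3+3, and 0.1765/2 = 0.088 in odds, or 8.1%, for entry 3+4. The mixture is 0.7 × 2.6% + 0.3 × 8.1% ≈ 4.2%, or about 3.8 events in 90 men.

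The ordinal comparator is a van Elteren test stratified by entry grade, with levels no cancer or ≤3+3, 3+4, and ≥4+3. With 2,000 simulated trials per cell, the simulation standard error is at most √(0.25/2000) ≈ 1.1 points.

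| Vaccine effect | Placebo ≥4+3 rate | Fisher | Ordinal, stratified |
|---|---|---|---|
| Common odds ratio 2 | 8% | 13% | 35% |
| Common odds ratio 2 | 14.5% | 20% | 43% |
| Common odds ratio 2 | 24.5% | 28% | 47% |
| Common odds ratio 3 | 8% | 24% | 67% |
| Common odds ratio 3 | 14.5% | 39% | 76% |
| Common odds ratio 3 | 24.5% | 55% | 83% |
| ≥4+3 halved, those men stay at 3+4 | 8% | 16% | 6% |
| ≥4+3 abolished, those men stay at 3+4 | 8% | 71% | 8% |

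Type I error of the ordinal test is 4-6%.

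**Stratifying the threshold test.** A Mantel-Haenszel test on ≥4+3, stratified by entry grade, raises power from 13% to 16% (odds ratio 2), from 42% to 47% (≥4+3 cut by 80%) and from 71% to 83% (≥4+3 abolished), with type I error near 5%. Part of this gain arises because the large-sample test is less conservative than Fisher's, so an exact stratified test would gain less.

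**The case against.** The threshold is a coherent choice. Since 3+4 is eligible, progression is defined as leaving the range that the protocol accepts at entry. Randomization protects the unadjusted comparison from bias, so using entry grade is a matter of efficiency. Clearance to no cancer is not lost, because 8.2.7 tests it. The objective is fifth of thirteen secondary objectives, all secondary analyses are exploratory, and no power is claimed. All of this stands, and it limits the weight of the point.

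The strongest objection is that the ordinal advantage comes from the assumed effect. A common shift at every grade boundary is the pattern that the ordinal test is built for. If the vaccine only keeps men from crossing into ≥4+3, the ordinal test has almost no power while Fisher keeps its own. This rules out replacing the threshold test or demoting it to description.

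A reader might also infer three stronger things that the documents do not support:

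- **That the endpoint ignores entry grade altogether.** The entry cap makes every event a true rise. What is missing is one-step movement and adjustment.
- **That the test rests on a handful of events.** No rate is given. The total is 4.5 to 9 at an assumed 5-10% and 18 to 36 at 20-40%, for a halving. The dutasteride trial's progression rates in 2.1 use another definition and a three-year horizon, so they cannot be borrowed.
- **That the test will almost always show no difference.** At an 8% rate, Fisher detects an odds ratio of 3 in about one trial in four, and complete prevention of ≥4+3 in about 71%.

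**Conclusion.** The point holds as a modest, inexpensive improvement. It is not an error that invalidates the endpoint. Objective 1.2.5 is broader than the one comparison specified for it: moves between 3+3 and 3+4 are not analysed, and the available entry grade is unused.

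For a roughly common shift in grade, the stratified ordinal test gains about 19 to 43 percentage points over Fisher across assumed placebo rates of 8% to 24.5% (47 − 28 = 19; 67 − 24 = 43). For an effect confined to the ≥4+3 boundary, it loses about 10 to 63 points at the 8% rate (16 − 6 = 10; 71 − 8 = 63). Neither test dominates, so both are needed. These sizes rest on assumed grade distributions, 30% entering at 3+4, 90 and 45 men biopsied, and no-cancer men counted as non-events. The gap between objective and endpoint needs none of these assumptions.

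**What to change.** In 8.2.5 and 13.5:

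1. Keep the ≥4+3 comparison as a formal test, but stratify it by entry Gleason (3+3 versus 3+4) with a Mantel-Haenszel or exact stratified test. Tabulate the proportions by entry grade, and state that men with no cancer on the post-intervention biopsy count as non-events, if that is the intention.
2. Add a prespecified exploratory analysis of ordered post-intervention grade (no cancer or ≤3+3, 3+4, ≥4+3), by a van Elteren test stratified by entry grade or a proportional-odds model adjusted for it.

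The cost is wording in two sections and one more exploratory test; 13.5 already applies no multiplicity correction to these. No new data are needed. The downside is that the ordinal odds ratio is less directly clinical than the ≥4+3 proportion and relies on a roughly common shift across grades, so the two results should be reported side by side.
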